One of the secondary outcomes, gingival blood flow, will be determined with the laser Doppler flowmetry (LDF) technique to measure the blood perfusion of the FGG donor site and as well as the contralateral side of the palate, as a positive control, at baseline prior to surgery, immediately after harvesting of the FGG from donor site, and on post-operative days 3, 7, 14 and 21. The LDF technique is an unbiased non-invasive method of monitoring the response to periodontal therapy. It is adequate for recording changes in gingival blood flow following periodontal surgery presenting different patterns of microvascular blood flow alterations during the wound-healing period. The LDF technique is based on the Doppler principle. A laser beam will be emitted by an optical fibre onto the FGG donor site. The light hitting moving erythrocytes is scattered back in shifting frequency, which is the Doppler effect, and is captured by one or more optical fibers. The light signals are then converted into electric signals and the resulting photocurrent is processed to provide a recording of the blood flow. The term used to describe blood flow is flux – a quantity proportional to the average speed of the blood cells and their concentration. This is expressed in arbitrary perfusion units (PU), which are linearly related to flux. The PeriFlux System 5000 (Laser Doppler Blood Perfusion Monitoring and  $\text{tcpO}_2/\text{tcpCO}_2$ ) along with the Laser Doppler Probes for the PeriFlux System 5000 will be used to perform the LDF technique.

The other secondary outcome will be the time needed to obtain a complete re-epithelialization of the FGG donor site, and will be performed by a non-invasive peroxide test. This test is based on the principle that if the epithelium is discontinuous, the  $\text{H}_2\text{O}_2$  diffuses into the connective tissue; the enzyme catalase acts on  $\text{H}_2\text{O}_2$  to release water and oxygen: this is clinically shown by the production of bubbles on the wound. 3%  $\text{H}_2\text{O}_2$  will be applied to the FGG donor site with a syringe and the appearance of bubbles will be recorded as a dichotomous variable (yes/no) at the post-operative days 3, 7, 14, and 21 until a subject's FGG donor site has

completely epithelialized (no bubbles observed), when they will not be measured again at future post-operative visits.

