#### *Surgical Procedures & Postoperative Care*

As stated above, periodontal residents under the direct supervision of periodontal faculty will perform the FGG procedure in all subjects. The FGG procedure will be performed following the surgical technique of Sullivan and Atkins or Miller. The donor tissue for the FGG procedure will be retrieved from either the right or left side of the palate. The FGG donor sites will be of a standardized size of 10 mm x 10 mm. As stated above, subjects in the control group will receive a hemostatic gauze, Surgicel®, covered by a cyanoacrylate dressing, PeriAcryl®90, at the donor site while the subjects in the test group will receive the same brand of hemostatic gauze, Surgicel®, but covered with episil®. Subjects in the test group will be given the remainder of the bottle of episil® with instructions for home application up to 3 times daily. Postoperative instructions will include discontinuing tooth brushing and flossing around the surgical site for the first 3 post-operative weeks. Subjects will be provided with a prescription for ibuprofen (600 mg) to take as needed for analgesia, unless contraindicated. Acetaminophen with 30mg of codeine will be prescribed to subjects unable to ingest ibuprofen.

The LDF measurements in the FGG donor site and on the contralateral side of the palate will be recorded in four sites. A clear acrylic stent will be fabricated for each subject from individual subjects' dental casts. Holes will be made in the stent in four locations on each the right and left sides of the palate. One site located centrally, one close to the mesial, one close to the distal and one close to the apical of the FGG donor site and in the same locations on the contralateral side of the palate will be measured at each of the specified postoperative appointments. The LDF measurement will be performed at baseline prior to surgery, immediately after harvesting of the FGG donor site, and on post-operative days 3, 7, 14 and 21. The LDF measurements will be performed with the tip of the fibre optic probe inserted into the holes of the individual acrylic stent. The LDF probe will be placed at a

standardized location perpendicularly to the tissues and at a distance of 0.5 mm from the tissues and will remain motionless during the LDF measurements.

Below is a summary of the timeline of the study:

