| Vital Signs   | ✓                       | ✓                               | ✓                              | ✓                              | ✓                               | ✓                               |
| Complete Visual
Analog Scale/
Questionnaire |                         |                                 | ✓                              | ✓                              | ✓                               | ✓                               |
| Doppler Flowmetry
(FGG donor site)              |                         | ✓                               | ✓                              | ✓                              | ✓                               | ✓                               |
| Doppler Flowmetry
(Contralateral side)          |                         | ✓                               | ✓                              | ✓                              | ✓                               | ✓                               |
| 3% H2O2
(FGG donor site)  |                         |                                 | ✓                              | ✓                              | ✓                               | ✓                               |

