#### *Statistical Analysis*

Descriptive statistics will be expressed as means+/- SD and frequency distributions. Intergroup (FFG donor site using episil® and Surgicel® (test) and FGG donor site with PeriAcryl®90 and Surgicel® (control)) comparisons at 1, 2, 3, 5, 7, 10, 14 and 21 days will be analyzed by the Mann-Whitney U test. The Wilcoxon signed-rank test will be used for intragroup comparisons between 1, 2, 3, 5, 7, 10, 14 and 21 days. Differences in frequency distributions between the episil® group and the PeriAcryl®90 group will be analyzed by the Fisher exact test. Associations

between pain VAS scores and the number of analgesic pills or number of days analgesics were taken will be examined by the Pearson correlation coefficient. The significance level for rejection of the null hypothesis will be set at  $\alpha = 0.05$ .

All LDF recordings, which may be impaired by artifacts caused by the relative motion of the probe, will be excluded. An average of the 2-minute period of each individual recording will be calculated. Changes of blood flux values in the FGG donor site will be expressed as the difference ( $\Delta PU$ ) between the PU value at a specific site at a specific observation time point ( $PU_t$ ) and the individual baseline value of the same site ( $PU_0$ ):  $\Delta PU_t - PU_0$ .

Descriptive statistics will be performed using the SPSS statistical software. The  $\Delta PU$  values in the FGG donor site will be analyzed using the general linear model (GLM) univariate test, after verification of the assumptions of homogeneity of variance and normality of the residual distribution. The observation time and point and the position (mesial, center, distal and apical to the FGG donor site) will be modeled as fixed factors and the patient as a random factor with the  $\Delta PU$  as the dependent variable. The Dunnett two-sided *t*-test will be used, in order to evaluate the differences between baseline and subsequent time points and between different positions in the FGG donor site during the overall observational period. Data will be presented as mean SE. Statistical significance will be accepted at  $p < 0.05$ .

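### The contralateral palate is measured as the LDF control on every occasion but has no role in the analysis, so planned time-versus-baseline contrasts cannot separate donor-site healing from visit-to-visit flow shifts

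*Combined protocol and SAP*

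**What the plan says.** Study Population and Design says flux is measured at the donor site "as well as the contralateral side of the palate, as a positive control", and gives the occasions as "at baseline prior to surgery, immediately after harvesting of the FGG from donor site, and on post-operative days 3, 7, 14 and 21". Surgical Procedures & Postoperative Care specifies four stent holes per side (central, mesial, distal, apical), "and in the same locations on the contralateral side of the palate will be measured at each of the specified postoperative appointments". The visit descriptions repeat the bilateral reading at each post-operative visit, and the timeline chart gives it a row of its own ("Contralateral side"), ticked from the day of surgery to day 21.

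Statistical Analysis is the only place where LDF analysis is described:

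- Endpoint: "Changes of blood flux values in the FGG donor site will be expressed as the difference" between the value at a time point and the baseline value of the same site.
- Model: the change "values in the FGG donor site will be analyzed using the general linear model (GLM) univariate test". On its terms: "The observation time and point and the position (mesial, center, distal and apical to the FGG donor site) will be modeled as fixed factors", with patient as a random factor.
- Comparisons: Dunnett tests "in order to evaluate the differences between baseline and subsequent time points and between different positions in the FGG donor site".

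There is no side term, no contralateral endpoint and no donor-versus-contralateral comparison. The Mann-Whitney and Wilcoxon tests are set at the eight pain days and do not mention the contralateral side.

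**The concern.** Flux is reported in arbitrary perfusion units, and the planned inference is change from baseline at one site. Such a change has at least two possible sources: the wound, and whatever else differs between that occasion and baseline. The contralateral palate is the only same-occasion reference the study collects that could tell them apart. As written, it is collected and left out.

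Two things are at stake. First, a significant change over time at the donor site could be reported as healing when it is a general shift in flow. Second, with no prespecified role for the control, the analyst can choose after seeing the data among donor-only, subtracted and adjusted results.

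**Working it through.** **No plan figure applies.** The plan gives no SD, effect size or power for LDF. Its detectable effects (f = .57, .67, .83 at n = 40, 30, 20) refer to change in pain score. They reproduce as a group-by-time interaction with six occasions (.575, .667, .826), a design the plan does not state, and they do not enter below.

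**Readings without a specified use.** 40 subjects × 6 occasions × 4 positions = 960 contralateral readings at most. Of these, 40 × 4 = 160 are baseline, leaving at most 800 changes from baseline, before dropout and artefact exclusion.

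**Step 1: time versus baseline, donor site only.** Assume no true healing change, residual SD 1 per reading, and a flow shift for each patient and occasion with SD s, shared by both sides and all four positions. The model fits time, position and patient. Take one contrast at two-sided 5%.

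- Residual df = 960 − 40 − 5 − 3 = 912.
- True variance of the contrast = (2/40)(s² + 1/4).
- Variance the model assigns = (2/160) × MSE, with MSE ≈ 1 + s² × (4 × 39 × 5)/912.
- For s = 0.5, the true SE is 0.158 and the model's SE is 0.123. For s = 1.0, they are 0.250 and 0.152.

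The patient effect does not absorb a shift shared by four positions on one occasion, so the model's SE is too small. An added mean shift also goes straight into the estimate.

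| s | Mean shift | False positives, donor only: formula | Simulated | Simulated, donor minus contralateral |
|---|---|---|---|---|
| 0 | 0 | 5.0% | 4.7% | 4.8% |
| 0.5 | 0 | 12.6% | 13.9% | 5.7% |
| 1.0 | 0 | 23.2% | 22.8% | 5.5% |
| 0 | 0.5 | 99.4% | 99.6% | 5.2% |
| 0.5 | 0.5 | 94.9% | 94.9% | 4.5% |
| 1.0 | 0.5 | 79.0% | 77.7% | 6.5% |

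The rows without a mean shift could be repaired by a patient-by-visit random effect, even with donor data alone. The rows with a mean shift could not; they need the control side. Dunnett's procedure corrects for the number of comparisons and does nothing about either problem.

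**Step 2: precision of a between-arm comparison.** Take one occasion, 20 per arm, two-sided 5%, noncentral t. The unadjusted detectable difference at 80% power is d = 0.909. Let r be the correlation of donor and contralateral change (assumed), with equal SDs.

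- Covariate adjustment: variance × (1 − r²), so d becomes 0.909/√(1 − r²).
- Plain subtraction: variance × 2(1 − r), so d becomes 0.909/√(2(1 − r)).

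| r | Variance cut, covariate | Power, covariate | Variance factor, subtraction | Power, subtraction |
|---|---|---|---|---|
| 0 | 0% | 80% | 2.00 | 51% |
| .3 | 9% | 84% | 1.40 | 66% |
| .5 | 25% | 90% | 1.00 | 80% |
| .7 | 49% | 98% | 0.60 | 95% |

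Subtraction gains only when 2(1 − r) < 1, that is, r > .5.

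**The case against.** **The control is not wholly ignored.** The artefact exclusion and the averaging over each recording can be read to cover all LDF readings, and general descriptive statistics are planned. That is true, but none of it is an endpoint, model term or comparison.

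**The LDF hypothesis is between randomised arms.** A reader might infer that visit-to-visit shifts bias the arm comparison. They do not: shifts common to both arms balance in expectation and add only noise. This objection stands and limits the attribution problem to the within-site contrasts over time. Those are, however, the contrasts the section actually plans.

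**The size of the shifts is unknown.** The stent, the perpendicular probe and the fixed 0.5 mm distance standardise the measurement, and motion artefacts are excluded. These steps limit positional error, not physiological change between occasions. Still, the documents give no shift size, so Step 1 shows a mechanism and not an expected error rate.

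**A precision loss is not established.** A reader might infer that leaving out the control certainly wastes precision. With an open wound on one side and intact mucosa on the other, a substantial correlation of changes cannot be presumed, and at r = 0 the gain is nil. This stands.

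**Adjustment carries its own risk.** Contralateral readings after surgery are post-randomisation. The test arm alone self-applies an oral spray at home, so the contralateral palate may be exposed in one arm only. The documents show no effect on flow, but they do not exclude one, and adjusting for a treatment-affected reading could distort the arm comparison. This stands and shapes the fix.

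**Conclusion.** The omission is clear from the text: a declared control, matched in position and occasion, has no role in the only LDF analysis described. It follows that the planned time-versus-baseline contrasts cannot separate donor-site healing from flow shifts between occasions. The false-positive figures rest on assumed shifts of 0.5 to 1.0 residual SD (random) and 0.5 (mean), fully shared by the two sides; a partly shared shift would be only partly removed.

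For the between-arm comparison, the supportable statement is that precision may be lost: between none and about half of the error variance for r from 0 to .7. The power figures are illustrative. They describe a single-occasion comparison that the plan does not contain, since its LDF model has no treatment term. That is a separate and larger gap, and closing it would not by itself bring the control readings in.

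The point concerns a secondary outcome and does not touch the pain analysis. It should be corrected before the LDF data are analysed.

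**What to change.** In Statistical Analysis:

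1. Compute the change from baseline for the contralateral side exactly as for the donor site.
2. For change over time, model both sides with side, time, position and side-by-time as fixed effects, and patient and patient-by-visit as random effects. Base the healing conclusion on donor versus contralateral change at the same occasion. If shifts may not be fully shared by the two sides, add a random effect for side within patient and visit.
3. For the between-arm LDF comparison, once a treatment term is in place, keep the unadjusted donor change as the main result. Prespecify a supporting analysis with same-visit, same-position contralateral change as a covariate. Do not offer plain subtraction as interchangeable for this comparison.
4. Tabulate contralateral change by arm, and show adjusted and unadjusted results together.

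The cost is wording and some extra tables; no visit or measurement is added. The remaining downside is that a treatment effect on the contralateral side would make the adjusted result hard to interpret, which is why item 4 is needed.

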**NCT03350724**

**Version Date: 10/06/2015**

*Protocol Title*

Patient Outcomes and Gingival Blood Flow using Laser Doppler Flowmetry  
Following the use of episil® on Free Gingival Graft Donor Sites

*Principal Investigator*

[name] M.B.A., D.M.D.

*Co-Investigators*

[name] D.D.S., M.S.

[name] B.D.S, M.S., M.S.D.

*Population*

The population will consist of 40 subjects, 18 years of age and over, females (non-pregnant or non-breast feeding) and males, with a general health status of ASA 1 or 2, and patients of record at UTHealth School of Dentistry in Houston, Texas requiring the gingival augmentation procedure, the free gingival graft. [Augmentation of gingival tissues may be considered an elective procedure. Elective surgical procedures are not routinely performed on pregnant and lactating women. Such procedures can be performed after childbirth and/or completion of lactation.] A total of 60 subjects will be consented to account for some subject's unwillingness or inability to continue in the study and non-compliance with study procedures and appointments.

*Number of Sites*

This will be a single site study at UTHealth School of Dentistry in Houston, Texas.

*Study Duration*

The duration of the study will be two years.

*Subject Duration*

The duration per subject will be three weeks.

*Background, Aim, & Hypothesis*

The free gingival graft (FGG) is a commonly used periodontal plastic surgery procedure for the augmentation of keratinized gingiva around teeth and implants. The FGG procedure uses a harvesting technique from the palate that leaves an open wound that heals by secondary intention, which can take 2 to 4 weeks. Mucogingival surgery has been shown to cause postoperative pain 3.5 times as much pain as osseous surgery and 6 times as much pain as soft tissue surgery. When bone is left exposed it tends to exaggerate the inadvertent postsurgical inflammatory response and increase postoperative pain. Wessel and Tatakis compared patient outcomes following subepithelial connective tissue graft (SCTG) and FGG procedures and indicated that FGG was associated with a greater incidence of donor site pain compared to SCTG donor site during the early postoperative period. There were significant differences between early (3-day) and late (3-week) pain levels for FGG donor sites. Pain in the palatal donor site at 3 days postoperatively was reported by

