A new wound dressing material, episil®, has shown to give rapid extended reduction of pain in cancer patients suffering from Oral Mucositis/Stomatitis (may be caused by chemotherapy or radiotherapy). The intended use of episil® is for the management of pain and relief of pain, by adhering to the mucosal surface of the mouth, soothing oral lesions of various etiologies. episil® has obtained 501(k) market clearance by the US FDA, in June 2011. episil® is an oromucosal liquid in a multi-dose container and is without active pharmaceutical ingredients and without systemic side effects demonstrated in clinical and pre-clinical studies. episil® is intended for use in the oral cavity as far as the pharynx but it is not dangerous to swallow. The oromucosal liquid transforms *in situ* to a bioadhesive oromucosal gel by uptake of small amounts of aqueous fluid. episil® contains six ingredients glycerol dioleate, soy phosphatidyl choline (lecithin), ethanol, propylene glycol, polysorbate 80 and peppermint oil which are all generally recognized as safe. No side effects have been reported. episil® contains small amounts of ethanol (alcohol), less than 100 mg per dose, which may cause a burning sensation when applied to sore mucosal surfaces. episil® contains also small amounts of propylene glycol which may cause skin irritation and peppermint oil which may cause allergic reaction. episil® should not be used on patients allergic to any of the ingredients, including peanuts, soy (soya) or peppermint oil. Currently there are no known concerns of use of episil® in human pregnancy or breast-feeding.

episil® is contained within an amber glass bottle with a manual metering pump filled with 10 mL of oral liquid. It is applied to the oral cavity by spraying 1 – 3 times. Distributed to affected areas in the mouth and within a few minutes the liquid converts to a gel and the protective film is formed. It is intended for use 2 – 3 times a day or as needed and is normally intended for continuous use for not more than 30 days.

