**Day 7 post-operative (4th clinic visit):** All subjects will bring completed Visual Analog Scale Form/Questionnaire to the day 7 post-operative appointment and will complete a Day 7 Post-Operative Visual Analog Scale Form/Questionnaire during that appointment and laser Doppler flowmetry readings will be performed on the free gingival graft donor site and on the contralateral side of the palate. 3% H2O2 will be applied to the FGG donor site with a syringe and the appearance of bubbles will be recorded as a dichotomous variable.

**Day 10 post-operative:** All subjects will complete at home the Day 10 Post-Operative Visual Analog Scale Form/Questionnaire.

**Day 14 post-operative (5th clinic visit):** All subjects will bring completed Visual Analog Scale Form/Questionnaire to the day 14 post-operative appointment and will complete a Day 14 Post-Operative Visual Analog Scale Form/Questionnaire and laser Doppler flowmetry readings will be performed on the free gingival graft

donor site and on the contralateral side of the palate. 3% H2O2 will be applied to the FGG donor site with a syringe and the appearance of bubbles will be recorded as a dichotomous variable.

**Day 21 post-operative (6th clinic visit):** All subjects will attend the day 21 post-operative appointment and will complete a Day 21 Post-Operative Visual Analog Scale Form/Questionnaire and laser Doppler flowmetry readings will be performed on the free gingival graft donor site and on the contralateral side of the palate. 3% H2O2 will be applied to the FGG donor site with a syringe and the appearance of bubbles will be recorded as a dichotomous variable.

Below is a chart of the timeline of the study:

| Procedure  | Visit
1
Screening | Visit
2
Day of
Surgery | Visit
3
3 Day
Post-op | Visit
4
7 Day
Post-op | Visit
5
14 Day
Post-op | Visit
6
21 Day
Post-op |
|--|-------------------------|---------------------------------|--------------------------------|--------------------------------|---------------------------------|---------------------------------|
| Medical History                                     | ✓                       | ✓                               | ✓                              | ✓                              | ✓                               | ✓                               |

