The outcome analysis of the time needed to obtain complete re-epithelialization of the FGG donor site will be made by comparing experimental groups on the frequency distribution of patients experiencing complete re-epithelialization in each of the 4 post-operative visits. The Williams-adjusted log-likelihood ratio was performed, followed by *post-hoc* tests using Bonferroni-corrected Fisher's exact test (2-tailed).

Based on a sample size of  $n = 40$  (20 per group), a repeated measures analysis will have 80% power to detect an effect size of  $f = .57$ . For a sample size of  $n = 30$  (15 per group), the same analysis will have 80% power to detect an effect size of  $f = .67$ , while a sample size of  $n = 20$  (10 per group) will have 80% power to detect an effect size of  $f = .83$ . All of these effect sizes are classified as large effects by Cohen's guidelines (1988), or large differences in the change in pain score between the two groups.

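### One no-bubble peroxide reading is taken as complete re-epithelialization and ends testing, so a false early closure can never be corrected

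*Combined protocol and SAP*

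**What the plan says.** Study Population and Design names the outcome: "The other secondary outcome will be the time needed to obtain a complete re-epithelialization of the FGG donor site". Bubbles are noted as present or absent at each of the four clinic visits after surgery, but only as long as the site still counts as open. Testing ends once it is "completely epithelialized (no bubbles observed), when they will not be measured again at future post-operative visits". The same paragraph explains that bubbles appear when peroxide passes through discontinuous epithelium and reaches connective tissue.

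The visit descriptions under Surgical Procedures & Postoperative Care say at each of days 3, 7, 14 and 21 that peroxide "will be applied to the FGG donor site with a syringe and the appearance of bubbles will be recorded as a dichotomous variable". The timeline chart ticks the test at all four visits. Neither repeats the stopping condition.

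Statistical Analysis uses the readings by "comparing experimental groups on the frequency distribution of patients experiencing complete re-epithelialization in each of the 4 post-operative visits", with two-tailed Bonferroni-corrected Fisher tests as the post-hoc step.

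Every donor site receives Surgicel, covered by PeriAcryl 90 in the control arm or episil in the test arm. Of episil, Background, Aim, & Hypothesis says that "the liquid converts to a gel and the protective film is formed". Test subjects also apply it at home, with supply for the whole study. The same section says that harvesting "leaves an open wound that heals by secondary intention, which can take 2 to 4 weeks".

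**The concern.** The test detects an open wound only if peroxide reaches exposed tissue. Material is placed over that tissue in both arms, and no visible text says that the site must be clear, or how a covered site should be read. An open wound under residual dressing could give no bubbles at day 3 or 7, earlier than the protocol's own healing time would lead one to expect. The stop rule then cancels the retest that could have shown the error.

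The two kinds of error are treated unequally. A false bubble reading is tested again at the next visit, but a false no-bubble reading before day 21 is not. Uncorrected errors therefore build up towards early closure. The arms differ in the covering material and in whether it is renewed at home, so the error rate could also differ by arm. Part of any healing difference could then reflect which covering hinders the test more.

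**Working it through.** The plan gives no sample size, closure rate or error rate for this outcome, so there is no stated figure to reproduce. The check asks what the rule does over a range of assumed error rates.

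**Inputs from the documents.** 20 per group; tests at days 3, 7, 14 and 21; stop at the first negative; two-tailed Fisher tests with Bonferroni correction. Over four visits the threshold is 0.05/4 = 0.0125.

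**Assumptions.** True closure is 0%, 0%, 30% and 80% at the four visits in both arms. An open site falsely reads negative with probability q, independently at days 3 and 7, with no errors at days 14 and 21. The Fisher tests are applied to cumulative closure. The preliminary Williams-adjusted test is not modelled.

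**Step 1: sites locked in by day 7.** All sites are truly open at both visits, so the share is 1 − (1 − q)².
- q = 5%: 1 − 0.95² = 9.75%, about 10%
- q = 10%: 1 − 0.90² = 19%
- q = 20%: 1 − 0.80² = 36%

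**Step 2: recorded closure at day 14.** The true value is 30%. The recorded value is 0.30 + 0.70 × (locked-in share).
- q = 5%: 0.30 + 0.70 × 0.0975 = 37%
- q = 10%: 0.30 + 0.70 × 0.19 = 43%
- q = 20%: 0.30 + 0.70 × 0.36 = 55%

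**Step 3: chance of at least one false group difference** (20,000 simulated trials per row). Retesting means that every site is tested at every visit and a later bubble reading overrules an earlier negative.

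| q, arm 1 | q, arm 2 | Stop rule | Retesting |
|---|---|---|---|
| 5% | 0% | 1.3% | about 1% |
| 10% | 0% | 9% | about 1% |
| 20% | 0% | 64% | about 1% |
| 10% | 5% | 2.3% | about 1% |
| 15% | 10% | 2.4% | about 1% |
| 20% | 10% | 7% | about 1% |
| 10% | 10% | 1.2% | about 1% |
| 20% | 20% | 1.4% | about 1% |

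**Step 4: where the 64% comes from.** At day 7 the unaffected arm has exactly 0 of 20 recorded closed. Against 0/20, a count of 6/20 gives two-sided p = 2 × C(20,6)/C(40,6) = 0.020, and 7/20 gives 2 × C(20,7)/C(40,7) = 0.008. Seven locked-in sites are therefore enough for significance. With a 36% locked-in share, that happens with probability 0.62. Day 14 alone contributes about 13%.

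**Step 5: errors that persist to day 21.** With q = 20% at all four visits in one arm only, the chance of a false difference is about 69% under the stop rule and 2% with retesting. Recorded day-14 closure under retesting is then about 41% against a true 30%, so retesting removes most of the false differences but not all of the bias.

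**The case against.** The strongest reply is that the harm is inferred. No text says that either dressing blocks peroxide, how long it stays in place, or that false negatives occur, and the protocol cites precedent for the test. A reader might infer that the healing comparison will be biased, or that it carries a 64% false-positive risk. The documents support neither. Both rate and arm difference are assumed, and the 64% needs no error at all in the other arm, although both arms are covered. That part of the reply stands.

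Three further points stand in part.
- A reader might infer that errors can run only towards early healing. That holds only for errors that cannot be corrected: a false bubble reading does delay recorded closure, but it is retested.
- A reader might see a contradiction between the stop rule and the visit schedule. The schedule omits the exception and does not withdraw it. The two texts should be aligned, but this is not a clash of rules.
- Retesting through renewed film may not reveal every open wound. Step 5 confirms a remaining bias, but it also shows that retesting still removes most false differences.

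It can also be said that testing until first closure is natural for an event not expected to reverse. That is reasonable if the reading is reliable, and nothing in the visible text secures this on a covered site.

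**Conclusion.** The point holds as a weakness in the measurement rule, conditional on false negatives occurring. It is certain from the text that one negative reading sets the analysed result and that, before day 21, it cannot be corrected. It is plausible but not shown that residual covering causes false negatives, or that it does so unequally.

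Under the stated assumptions, 10% to 36% of sites are locked in as closed by day 7 for q from 5% to 20%. The effect on false group differences depends on the contrast between arms: negligible if the rates are equal, about 7% for 20% versus 10%, and large only if one arm is affected alone at a high rate. Equal rates still make recorded healing too early in both arms. The pain outcome and the blood-flow outcome are untouched. The change is worth making because it is cheap and the lost readings cannot be recovered afterwards.

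**What to change.** In Study Population and Design, delete the stopping condition and test every site at days 3, 7, 14 and 21, as the visit descriptions and chart already list. Define the closure visit as the first no-bubble reading that no later bubble reading contradicts. Add a form field for visible dressing, gel or hemostat over the site at the time of the test, and code a covered no-bubble reading as not assessable. Report closure by first negative reading as a sensitivity analysis.

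The cost is a few seconds of testing at visits subjects already attend, one form field, and some readings lost as not assessable. A late false bubble can move recorded closure later, which the sensitivity analysis would show. Closure first seen at day 21 stays unconfirmed, and some bias remains if film that is not visible still hinders the test at days 14 and 21.
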